The DVD process interview will assess receipt of, viewing of, and satisfaction with the DVD and will be done approximately 2 weeks post-mailing of the DVD. Receipt, experience and satisfaction with the PN intervention, for those randomized to the DVD+PN group, will be assessed as part of the 6 month interview (T2). The 6 month interview will also assess changes in knowledge, patient activation, CRC fear, cancer fatalism, and colonoscopy-related procedural anxiety. Health beliefs for colonoscopy and FIT will be assessed as will self-reported CRC screening intention, uptake and satisfaction with the screening experience (for those who completed screening). At 9 months, we will assess self-reported CRC screening intention, uptake and satisfaction with the screening experience (for those who completed screening since T2). Participants will receive a \$50 gift card for the baseline interview, a \$50 gift card for the 6 month interview and a \$50 gift for completing the 9 month interview; a total of \$150 for participants who complete all three interviews. Participants who complete the additional DVD process interview will receive another \$50 gift card for a total of \$200 in gift cards. By using gift cards with an appealing dollar amount over the 9 month data collection period, we hope to incentivize participants to remain in the study. Additional retention strategies which we will use include mailing

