**PRIMARY OUTCOME MEASURES: (RQ-6, PC-2, IR-4)**

**Completion of any CRC screening test** (fecal immunochemical test (FIT) or colonoscopy) will be measured by medical record review. FIT and colonoscopy completion dates will be extracted from the electronic medical record. Because self-report of CRC screening has correlated well with medical record data, we will also use validated items from our previous research to ask participants if they have had a CRC screening test (FIT or colonoscopy) as well as their plan to have one in the next 6 months (only for those who have not yet completed screening).

**Quality of bowel preparation** will be assessed two ways for those participants who attend their colonoscopy: 1) by participant self-report of their bowel prep experience and 2) via review of electronic medical records. When patients arrive in the endoscopy department, a nurse assesses their experience with the bowel preparation and adherence to dietary restrictions. Patients who report they were unable to complete the bowel prep or have eaten in the past 24 hours are considered inadequately prepped for the procedure and sent home. These patients must repeat the preparation to cleanse the bowel and reschedule their colonoscopy. For those who report successful completion of the bowel prep and adherence to dietary restrictions, quality of the bowel preparation (i.e. degree of cleanliness/emptiness of the bowel) is evaluated by the endoscopist during the colonoscopy. Standard practice is to evaluate bowel preparation quality using an assessment similar to the Aronchick 5-point scale where 1=*excellent*, 2=*good*, 3=*fair*, 4=*poor*, and 5=*inadequate*. Adequate is a term that may also be used to describe the quality of bowel preparation as a single descriptor or in addition to the Aronchick assessment as excellent (1), good (2), or fair (3). Procedural notes including endoscopists' ratings of the quality of the bowel prep are entered into ProVation, a menu-driven software program. Therefore, participants will be considered inadequately prepped if they are: 1) deemed inadequately prepped from self-report during initial nursing assessment OR 2) if the endoscopist rates the quality of the bowel prep as poor (4)

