For Aim 1, we will test the primary hypothesis related to comparing intervention effects among the three randomized groups (H1.1: PN+DVD vs. DVD only and H1.2: PN+DVD vs. usual care and DVD only vs. usual care) using the outcome of completion of CRC screening using any test at 12 months post-baseline. In addition, quality of bowel preparation, procedural anxiety, and satisfaction with the screening experience will be examined as outcomes. As an initial assessment of CRC screening completion at 12 months, we will use a chi-square test for a 3 x 2 (group by screening completion) contingency table to test whether completion rates differ across groups. If the  $p$ -value for the overall test is significant at the .05 level, pair-wise 2 x 2 tests will be conducted at the  $.05/3 = .017$  level. However, the primary analyses for Aim 1 will involve fitting multivariable logistic regression models of the primary outcome of 12-month CRC screening test completion (yes/no). Independent variables will be group assignment and continuous and categorical individual characteristics. These models will also allow us to investigate intervention effects on CRC screening test completion while adjusting for potential confounders. Group assignment will be coded using dummy variables with usual care as the reference category. For H1.3, quality of bowel preparation will be analyzed for those participants who complete colonoscopy with proportional-odds ordinal logistic regression using an ordinal dependent variable ( $1 = \text{excellent}$ ,  $2 = \text{good}$ ,  $3 = \text{fair}$ ,  $4 = \text{poor}$ ,  $5 = \text{inadequate}$ ). If some outcome categories are sparse, the outcome will be dichotomized into adequate

(*excellent or good*) versus inadequate (*fair, poor, or inadequate*). The outcomes of anxiety and satisfaction are continuous outcomes and will be modeled with linear regression.

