**Aim 2. Examine age, race/ethnicity, sex and income as potential moderators of intervention effects. (RQ-4, HT-1, HT-2, HT-3, HT-4)** We will fit multivariable models as in Aim 1, except now including interaction terms for age (< 65, age 65+), race/ethnicity (Non-hispanic Black, Non-hispanic White), sex (male, female), and annual income (<\$15,000, ≥\$15,000), respectively. Moderators will be identified by significant interaction terms in regression models. The key moderation effects of interest will be between PN+DVD vs. DVD only. Moderation of PN+DVD vs. usual care, and DVD only vs. usual care also will be examined. Hispanics will be excluded from race/ethnicity interaction tests due to small sample sizes.

**Aim 3. Examine changes in knowledge and health beliefs (knowledge, perceived risk, perceived benefits, barriers, and self-efficacy) as potential mediators of intervention effects. (RQ-6)** Mediation analysis will be conducted to identify potential mediators. Specifically, for each of the variables (changes in knowledge, perceived risk, perceived benefits, perceived barriers, and self-efficacy) mediation effects will be estimated in an logistic regression setting, fitting the appropriate mediation models using MPlus and then testing indirect effects using the percentile bootstrap approach to estimate the indirect effect. We will fit models that estimate the effects of PN plus DVD vs usual care and DVD only vs usual care, and also models that compare the strength of the indirect effects between the PN plus DVD and DVD only arms. We expect to see a difference in mediation effects mainly on barriers, with the PN plus DVD having a greater mediation effect on barriers than DVD only.

**C.14. Potential problems, strategies and benchmarks for success.** Potential problems are described below along with plans to minimize them. (*IR-6, MD-1, MD-2, MD-4*)

- *Loss to follow-up:* It is anticipated that there will be some loss to follow-up because of participant dropout, death, or relocation. Based attrition data through May 31,2019 , we estimate the loss to be approximately 25% over the 9-month study period, which has been accounted for in the revised power analysis and sample size determination.
- *Limited internal validity:* Randomization will minimize the influence of extraneous variables on outcomes.

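### Aim 3 sets no time order: if it uses the 12-month outcome, beliefs are measured after the outcome in everyone screened before 6 months, so mediation can be declared where none exists

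*Combined protocol and SAP*

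**What the plan says.** - **Mediators.** Section C.13, Aim 3, lists "changes in knowledge, perceived risk, perceived benefits, perceived barriers, and self-efficacy". Each goes into a logistic mediation model, and the indirect effect is tested with a percentile bootstrap.
- **When they are measured.** Table 3 marks knowledge and health beliefs at baseline and at 6 months, and at no later point. Section C.8 agrees: "The 6 month interview will also assess changes in knowledge", and in the same interview "Health beliefs for colonoscopy and FIT will be assessed as will self-reported CRC screening intention, uptake and satisfaction with the screening experience". The list for the last interview contains no mediator: "At 9 months, we will assess self-reported CRC screening intention, uptake and satisfaction with the screening experience".
- **Outcome.** Aim 3 states no window. Aim 1 in the same section is tested "using the outcome of completion of CRC screening using any test at 12 months post-baseline".
- **Dates.** Section C.9: "FIT and colonoscopy completion dates will be extracted from the electronic medical record". Aim 3 does not use these dates, and it neither lags the outcome nor separates people screened before T2.

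**The concern.** The plan expects screening well before 6 months. Participants are asked to view the DVD within 2 weeks (C.6), and the first navigator call comes about 2 weeks after mailing (C.4.b). Colonoscopy is usually booked within 4–5 weeks of referral (C.4). T2 itself asks about uptake, and records are reviewed at that point (Table 3). An earlier trial in the same health system, described in Section B.1, had 26% against 18% screened at 6 months.

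Having done a test can itself move these scales. The self-efficacy items, for example, ask how sure a person is of managing each step of the test. A T2 score taken after screening may therefore partly reflect the screening. Change scores do not remove this, because the T2 value already contains the shift.

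Aim 3 is meant to show how the interventions work. They are built to move these beliefs, so the first path (intervention to belief) may well be real. A second path (belief to screening) that partly runs backwards is then enough to produce a significant indirect effect.

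**Working it through.** **The plan's own figures.** The plan gives no error rate for Aim 3. The nearest figure is 80% power for the indirect effect with 115 per group (C.12). It cannot be confirmed or refuted, because the scale of the paths .2 and .39 is not given. With 230 people in two arms, a Sobel simulation gives 84% if both are standardised paths, and 30% if .2 is a between-arm difference in SD. It is not disputed here. The screening rates used below are those of Table 4. Its powers reproduce at α = .017 with a continuity correction: 92.2%, above 99.9% and 81.0%, against the stated 92%, 99% and 80%.

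**Inputs from the documents.** 115 per arm; screening 44% (DVD plus navigation), 20% (DVD), 5% (usual care).

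**Inputs that are assumptions.** f, the share of screening done before T2; d, the shift in the T2 belief caused by having been screened (SD); a, the intervention effect on the belief (SD).

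**Setup.** The mediator has no effect on screening, so any mediation declared is false. The comparison is DVD plus navigation against usual care.

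**Hand calculation.**
1. Apparent first path: the arm difference in the T2 belief is a + f·d·(0.44 − 0.05), with SE √(2/115) = 0.132.
2. Apparent second path: within an arm, screened and unscreened people differ by f·d on the belief. With SD near 1, the logistic slope per SD is about f·d. Its SE is about 1/√{115·(0.44·0.56 + 0.05·0.95)} = 1/√33.8 = 0.172.
3. A false claim needs both paths to be significantly positive, so its chance is roughly the product of the two probabilities P(Z > 1.96 − estimate/SE).

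Example with f = .5, d = .5, a = .4. First path 0.4 + 0.0975 = 0.4975, z = 3.77, probability .965. Second path 0.25, z = 1.45, probability .306. Product 30%.

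Results at d = 0.5, beside simulated rates (linear mediator model, logistic outcome model, percentile interval for the product of paths):

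| f | a | First path | Its probability | Second path | Its probability | Product | Simulated |
|---|---|---|---|---|---|---|---|
| .5 | 0 | 0.0975 | .111 | 0.25 | .306 | 3% | 2% |
| .5 | .2 | 0.2975 | .616 | 0.25 | .306 | 19% | 13% |
| .5 | .4 | 0.4975 | .965 | 0.25 | .306 | 30% | 29% |
| .7 | 0 | 0.1365 | .177 | 0.35 | .530 | 9% | 7% |
| .7 | .2 | 0.3365 | .723 | 0.35 | .530 | 38% | 32% |
| .7 | .4 | 0.5365 | .982 | 0.35 | .530 | 52% | 49% |

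The product is a rough guide and runs slightly high; the simulated column is the one to use. At d = 0.3, over the same f and a, the simulated range is about 0.5–20%. With no reverse effect the rate is at or below about 2.5%.

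**DVD against usual care.** Bootstrap runs of 150–200 trials per cell, counting both directions, gave 2% (a = 0) and 11% (a = .2) at f = .5, d = .5. At f = .75, d = .5 they gave 2% and 15–18%.

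**Landmark model** (people unscreened at T2, outcome after T2). At d = 0.5 and a = 0.4, false mediation for DVD plus navigation against usual care falls to 1–2%. The smaller bootstrap runs gave 1–10% over the three comparisons, with the highest values for DVD against usual care.

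**The case against.** Five points on the other side have weight.

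- **The belief may have changed first.** A reader might infer that, for those screened early, the mediator itself comes after the outcome. The documents support only that its *measurement* does. People may have watched the DVD and spoken to the navigator before testing, so true mediation is not excluded. This stands; what remains is that the planned model cannot tell the two apart.
- **The window is inferred.** Aim 3 does not say 12 months. This stands as a qualification. Table 5 in C.12 carries a 9-month label, but a window running from baseline to 9 months would raise the same problem.
- **The size rests on assumptions.** The intervention effect on the belief matters as much as timing and shift. With no such effect, or a weak shift, the inflation is small or absent. This stands, so the upper figures must not be read as expected values.
- **The mediators differ.** Benefits, barriers and self-efficacy have separate FIT and colonoscopy scales, while the outcome is either test, so a FIT need not move the colonoscopy scale. A reassuring result could lower perceived risk, and the bias could then hide mediation. This stands.
- **The plan is cautious already.** It speaks of potential mediators and allows sensitivity analyses as needed (C.13). That wording says nothing about time order, so it does not answer the point.

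**Conclusion.** The concern holds in a limited form. If Aim 3 uses the 12-month outcome, the planned model cannot separate a belief that led to screening from a belief changed by screening, and can declare mediation where none exists.

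For DVD plus navigation against usual care, with a mediator that does nothing and a 0.5 SD shift, the false rate is about 2–29% with half of screening early and 7–49% with 70% early, for an intervention effect on the belief of 0 to 0.4 SD. At a 0.3 SD shift it is about 0.5–20%. The nominal one-direction rate is 2.5%. All three inputs are assumptions. The early share will be known from the trial's own data; the shift caused by screening will not.

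Two stronger readings are not supported. The documents do not show that false mediation is likely for every mediator or every comparison. Nor does the point touch Aim 1, whose outcome and comparisons do not involve these measurements.

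**What to change.** In the SAP text for Aim 3:

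1. State the outcome window.
2. Use the extracted test dates to report, by arm, the share of participants screened before their T2 interview.
3. For each mediator, pre-specify a landmark sensitivity model: participants unscreened at T2, outcome = screening after T2. Report it beside the planned model.
4. Describe the all-events model as associational, and say that the direction of bias may differ by mediator, notably for perceived risk.

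The landmark model should not be a veto on mediation claims, because it has little power and uses a selected group. Expected events per 115 are 115 × .44 = 50.6 with navigation and 115 × .05 = 5.75 in usual care. After T2 this leaves 25.3 and 2.9 if half of screening is early, or 15.2 and 1.7 if 70% is. With true mediation (0.4 SD effect on the belief, odds ratio about 2 per SD, no reverse effect), detection for DVD plus navigation against usual care falls from 84% to 52% at half early, and from 82% to 28% at 70% early. Restricting to people unscreened at T2 also drops those who responded fastest, more of them from the navigated arm, so the arms compared are no longer fully protected by randomisation.

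The cost is SAP wording and one more model per mediator. No new data are needed.

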## D. Project Timeline and Milestones

Activity by Quarter: Beginning with July 2016	Q1	Q2	Q3	Q4	Q1	Q2	Q3	Q4	Q1	Q2	Q3	Q4	Q1	Q2	Q3	Q4	Q1	Q2 (NCE: 6 Mo)
Finalize protocol/ IRB approval	X																	
Registration of trial on clinical trials.gov	X																	
Advertise/hire research staff	X																	
Training research staff	X	X																
Intervention refinement	X	X	X															
Stakeholder/Comm. Advisory Board meetings	X	X	X	X	X	X	X	X	X	X	X	X	X	X	X	X		
Intervention pre-testing			X															
Development/testing of databases		X	X															
Participant enrollment (n=450)					X	X	X	X	X	X	X	X	X	X				
Completion of 25% of enrollment (n=113)								X										
Completion of 50% of enrollment (n=225)									X									
Completion of 75% of enrollment (n=338)										X								
Completion of 100% of enrollment (n=450)													X					
Baseline interviews, intervention delivery					X	X	X	X	X	X	X	X	X	X	X			
Process evaluation interviews					X	X	X	X	X	X	X	X	X	X	X			
6 month interviews							X	X	X	X	X	X	X	X	X			
9 month interviews								X	X	X	X	X	X	X	X			
Medical record audits									X	X	X	X	X	X	X	X		X
Data cleaning and preliminary analyses										X	X	X	X	X	X			
Analysis, write-up, dissemination													X	X	X		X	X
Datasets and codebooks prepared for sharing																	X	X
PCORI Reports		X		X		X		X		X		X		X		X		X

**Meetings** of investigators and stakeholders will be on-going throughout the study period. All investigators will attend monthly research team meetings. Clinical and patient stakeholders will meet with investigators every other month during the first 9 months of the study. Stakeholder meetings will be held quarterly throughout the remainder of the funding period. Other milestones are reflected in the timeline and include:

- **Start-up** will occur during the first 2-3 months of the proposed project and will involve finalizing the study protocol, obtaining IRB approval, and hiring and training research staff. In addition, the patient navigation and tailored DVD interventions will be refined, with patient navigators hired and trained, during the first 9 months.
- **Participant enrollment and baseline data collection** will begin in Month 13 and continue for 24 months, accruing approximately 20 participants per month or 5 each week.
- **Intervention delivery** will begin in month 14 and continue for 28 months
- **Follow-up data collection** will occur at 6 months after the baseline interview (T2) and at 9 months post-baseline (T3). Process interviews also will be conducted to assess receipt, viewing (of the DVD), and satisfaction with the interventions.
- **Data analysis**, reports, abstracts, and publications will be prepared during the final 15 months of the study.
- **A 6 month no cost extension period** will allow us to complete the 12 month EMR review, conduct data cleaning and analyses, and prepare the Final Progress Report.

## E. Patient Population (RQ-2, RQ-3, RQ-4, PC-1, PC-2)

**E.1. Sample and eligibility criteria.** 450 people who canceled or did not attend their colonoscopy appointment will be enrolled in this study. Participants will be eligible if they are 50-75 years old if non-African American or 45-75 years old if African American and were referred to Eskenazi's endoscopy unit for a colonoscopy. Stratified block random assignment to each of three groups will be performed within 12 strata formed by crossing sex, three race/ethnicity groups, and two age levels (male/female, Black/White/Hispanic, age<65/age 65+) to ensure that the three randomized groups are comparable in distribution of sex, race/ethnicity, and age. At the completion of the baseline interview, patients will be randomly assigned to the tailored DVD-only group, the tailored DVD plus patient navigator group, or usual care. Based on the 65% participation rate we achieved in our recent R01 conducted in this same health system, we conservatively estimated our participation rate at 55%. However, our actual, cumulative participation rate for eligible subjects was 75% through May 31, 2019. Therefore, we will need to contact approximately 600 eligible people to enroll 450. Data from 2014

indicate the availability of 1150 potentially eligible patients during that 12 month period (See Table 6). An estimated 2200 would be available over the 24 month enrollment period. Based on our preliminary studies, no more than 20% attrition was anticipated at 9 months. Actual data from Year 3 of this project as of May 31, 2019 shows an attrition rate closer to 25% at the 6 month follow-up timepoint. This approximate 25% rate is being used in re-calculating the sample size required.

**Table 6. Colonoscopy orders, completion rates and non-completion rates by race/ethnicity and gender**

Race/ethnicity	Colonoscopies ordered		Colonoscopies completed		Colonoscopies NOT completed	
	N	%	N	%	N	%
Black/African American	1254	64%	505	40.3%	749	59.7%
White/Caucasian	664	34%	280	42.2%	384	57.8%
Hispanic	44	2%	26	59.1%	18	40.9%
Sex: Male	806	41%	324	40.2%	482	59.8%
Female	1156	59%	487	42.1%	669	57.9%
Total	1962	100%	811	41.3%	1151	58.7%

**E.2. Study Site, Colonoscopy Referral, and Scheduling Process.** Patients who have been scheduled for, but not completed, colonoscopy at the endoscopy department in our local safety net health system will be recruited. The Eskenazi Endoscopy Department has 4 procedure rooms and is staffed each day by 2-3 gastroenterologists. In a recent 12-month period, 5,702 procedures were performed, with an average of 20-35 scheduled daily. Colonoscopy referrals come from nine clinics/community health centers that comprise the Eskenazi Primary Care Network/ Community Health Centers. Eskenazi Community Health Centers see approximately 205,000 patient visits/ year, with 50% of visits financed by Medicare or Medicaid and 40% financed by the county indigent care health insurance program or self-pay. The indigent care program provides financial assistance to patients at or below 200% of the federal poverty level who have inadequate or no healthcare coverage. The Eskenazi clinics and endoscopy department use an integrated electronic medical record (EMR) system as their clinical data repository for patient care. Primary care providers enter referrals (orders) for colonoscopy into the EMR and patients are automatically scheduled using an open access system (i.e., no appointment with a gastroenterologist required). The referral is sent electronically via the EMR from the primary care clinic to the endoscopy unit. Within one week, patients receive a letter with their colonoscopy appointment date/time along with written instructions for preparing for the test and for rescheduling if they cannot attend. Reminder calls are placed by an endoscopy nurse 1-2 days prior to the appointment. Most of the cost for colonoscopy is covered by the indigent care program. Patients with commercial or governmental coverage pay the amount specified by their insurer; those without insurance who have household incomes below 200% of poverty are eligible for the indigent care program and pay \$40 for colonoscopy. Patients without insurance who do not qualify for the indigent care program pay 50% of the cost at the time of scheduling and 25% after the test is complete.

**E.3 Recruitment.** Trained study staff will recruit participants using procedures consistent with clinic and HIPAA requirements. On a weekly basis, Eskenazi Health IT department will generate lists of age-eligible patients at average risk who did not attend their colonoscopy appointment. The list will include 2 groups of average risk patients who missed their appointment: 1) patients who had a colonoscopy screening ordered; and 2) patients who had a recent fecal immunochemical test (FIT) that was positive with a follow-up order for colonoscopy. Due to differences in physician ordering practices, the follow-up colonoscopy can be ordered as a colonoscopy screening, colonoscopy diagnostic, or colonoscopy high risk. Patients will be approved for contact by [name], Director of the Eskenazi Health Endoscopy Department. Patient information will be released to the study's data manager, the Eskenazi Endoscopy Department's Patient Navigator nurse, and trained research staff at the IU School of Nursing using secure electronic data transfer methods. Information disclosed is limited to that which is necessary to determine eligibility and to contact patients by mail and telephone. As a first step, the Endoscopy Patient Navigator nurse will screen patients by looking back 10 years and excluding any with a history of adenomatous polyps, sessile serrated polyps, or any mass suggestive of neoplasia. Patients with a history of hyperplastic polyps, lymphoid tissue, or no polyps will be recruited. Research staff at the IU

School of Nursing will send introductory letters, signed by the Principal Investigator and a co-investigator who is a member of the Eskenazi Medical Staff, along with a recruitment brochure and Study Information Sheet that explains the study to all approved patients. The letter informs patients that they will receive a phone call about the study within the next week unless they call a toll-free number to indicate they do not wish to be contacted. One week after letters are mailed, trained recruiters at the School of Nursing will contact potentially eligible participants who have not called the toll-free number. Recruiters will explain the study and answer questions about study requirements, potential risks, and compensation. Adequate speech, hearing, and cognition of potential participants will be confirmed by recruiters based upon the phone conversation. They will then proceed to determine eligibility, obtain both verbal informed consent and verbal HIPAA Authorization, and schedule a convenient time to conduct the baseline interview. Each participant who is not reached will be called back up to, but no more than, 10 times. Recruiters will document each call attempt including the date, time, disposition, and callback preference. Participants who decline to participate will be thanked for their time, with their response and reason for refusal recorded. Proposed recruitment procedures have been previously tested and found to be successful in our prior studies. Any unanticipated challenges to recruitment will be discussed with the research team, our CAB and clinical stakeholders.

